As MATCH has approached its goal of sequencing ~6000 patient tumors, this section incorporates changes to expand eligibility criteria (effective since Addendum #3) to allow patients from select sites who potentially undergo tumor profiling through non-MATCH assays and to increase the accrual goal (effective since Addendum #6). In this section, patients who enter COMET through MATCH Step 0 (prior to or after the activation of this addendum allowing for eligibility expansion) will be referred as the MATCH cohort, and other patients (who enter after the corresponding addendum activates) will be referred as the non-MATCH cohort.

7.1 Primary Study: Randomized Study of Web-based Pre-disclosure Genetic Education versus Usual Care (Step 1 – Arms A & B)

Rev. 2/17

NOTE: Patients on Arm C (see Section [□□□□](#)) will not participate in or complete any primary study (Step 1) education or surveys, and will immediately be registered to Arm E and complete all of the substudy (Step 2) procedures.

Rev. 7/17

7.1.1 *Primary endpoints* will include change in knowledge and distress (state anxiety, Promis anxiety, Promis depression and cancer specific distress) from baseline to post-education (T0 to T1) and baseline to post-disclosure (T0 to T2).

The following 10 analyses are of primary interest: change scores from T0 to T1, and T0 to T2 of each of the following five outcomes: knowledge, state anxiety, cancer specific distress, Promis anxiety and Promis depression, which correspond to 10 primary analyses. To account for the 10 primary analyses, A Bonferroni correction is considered here, setting the nominal p-value to declare statistical significance of $p < 0.005$ (5% Typical Type I error rate / 10 comparisons = 0.5% nominal p-value for declaring statistical significance). Preliminary data from the COMET pilot study (State Anxiety, IES-Total, Knowledge) is used to calculate power. As there was no preliminary data for Promis Depression/Anxiety in a similar setting, power calculation for these two measurements are based on data reported in Hinds et al. (2012). A sample size of 200 (with evaluable paired data) /arm is chosen here, which provides at least 85% power for all short-term outcomes (e.g. T0-T1) and changes in knowledge and cancer specific distress after receipt of tumor profiling results (e.g. T0-T2), using t test at two-sided 0.005 significance level.

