With the completion rate for both T0 and T1 surveys at approximately 60% (as analyzed in May 2018) and the goal of evaluable sample size at 200/arm (at least for the analysis of changes between T0 and T1), the accrual goal of the primary intervention study needs to be inflated from 400 to 670 patients in order to maintain sufficient power for detecting proposed changes from T0 to T1 and changes in knowledge and cancer specific from T0 to T2 (as described in the preceding paragraph). With the completion rate for both T0 and T2 surveys at approximately 45% (as analyzed in May 2018), the projected evaluable sample size of 150 patients/arm can give the power of 72% for changes in knowledge and 95% for changes in cancer specific distress from T0 to T2. These 670 patients will be randomized 1:1 between the two arms, and the randomization will be stratified by gender, race, age (> 65 vs. ≤ 65), and education level. As of this analysis time, 320 patients have been enrolled into the primary intervention study. The current COMET accrual rate is approximately 15 patients per month (based on the last 3 months). Assuming 15, 20 or 25 patients per month (as more expansion sites are added over time) can be accrued to COMET from the select sites, it is expected to take 23, 17 or 14 additional months, respectively, to complete Step 1 accrual of 670 patients.

The original accrual plan posed a limitation on White patients at 80% of the accrual goal to ensure diversity of patients. Given that the accrual of this study might terminate early if the funding of this study ends, the accrual limitation on White patients is being lifted to ensure the maximal number of patients enrolled before funding ends.

Power for various sample sizes

Variable	Change score time period	Sample Size Per Arm	Power for p< 0.005, 2-sided	Change Score Group 1	Change Score Group 2	Standard Deviation Group 1	Standard Deviation Group 2
State Anxiety	T0 to T1	100	98%	2.71	-2.78	8.24	7.43
State Anxiety	T0 to T1	150	100%	2.71	-2.78	8.24	7.43
State Anxiety	T0 to T1	200	100%	2.71	-2.78	8.24	7.43
State Anxiety	T0 to T1	300	100%	2.71	-2.78	8.24	7.43
State Anxiety	T0 to T1	400	100%	2.71	-2.78	8.24	7.43
State Anxiety	T0 to T1	61	85%	2.71	-2.78	8.24	7.43
IES-Total	T0 to T1	100	100%	0.29	-1.78	1.70	3.19
IES-Total	T0 to T1	150	100%	0.29	-1.78	1.70	3.19
IES-Total	T0 to T1	200	100%	0.29	-1.78	1.70	3.19
IES-Total	T0 to T1	300	100%	0.29	-1.78	1.70	3.19
IES-Total	T0 to T1	400	100%	0.29	-1.78	1.70	3.19

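### Section 7.1.1 lists T0–T2 knowledge among the analyses whose power 670 patients maintain, but at the plan's own 45% completion rate that analysis has 72% power, not the 85% referred to (a minor wording contradiction)

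*Combined protocol and SAP*

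**What the plan says.** All of this is in Section 7.1.1 of the combined protocol and SAP.

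- **Primary family.** "The following 10 analyses are of primary interest: change scores from T0 to T1, and T0 to T2 of each of the following five outcomes". The T0–T2 comparison of knowledge is therefore one of the ten primary analyses, each tested at the two-sided 0.005 level.
- **Evaluable target.** "A sample size of 200 (with evaluable paired data) /arm is chosen here", and it is said to give "at least 85% power for all short-term outcomes (e.g. T0-T1) and changes in knowledge and cancer specific distress after receipt of tumor profiling results".
- **Accrual goal.** The next paragraph takes the roughly 60% rate of completing both T0 and T1, keeps 200 per arm as the evaluable goal (at a minimum for the T0–T1 changes), and raises accrual from 400 to 670. The stated purpose is to "maintain sufficient power for detecting proposed changes from T0 to T1 and changes in knowledge and cancer specific from T0 to T2", with a parenthesis pointing back to the preceding paragraph.
- **Projected T0–T2 yield.** The following sentence gives about 45% completion of both T0 and T2, and says that "the projected evaluable sample size of 150 patients/arm can give the power of 72% for changes in knowledge" and 95% for cancer-specific distress.
- **Power table.** For T0–T2 knowledge the table prints 72% at 150 per arm, 85% at 194 and 86% at 200.

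**The concern.** The accrual sentence names T0–T2 knowledge as an analysis whose power 670 patients maintain. The level it refers back to is at least 85%, and that level depends on 200 evaluable patients per arm. The 670 delivers 200 per arm at T1 but only about 150 at T2. For this one analysis, the claim that power is maintained and the 72% in the next sentence cannot both stand.

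At stake is how a null result would be read. Someone relying on the accrual sentence would take the T0–T2 knowledge test to have at most a 15% chance of missing the planned effect. On the plan's own projection that chance is about 28%. The text does not say that the 85% level was given up for this analysis, or that 72% was judged acceptable.

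**Working it through.** **Inputs, all from Section 7.1.1 and its power table**
- Two-sided alpha 0.005, so the normal critical value is 2.807.
- T0–T2 knowledge: change scores 5.86 and 4.40 (difference 1.46), SDs 4.30 and 3.05.
- T0–T2 cancer-specific distress (IES-Total): change scores −1.00 and −2.17 (difference 1.17), SDs 1.53 and 2.86.
- Completion 60% (T0 and T1) and 45% (T0 and T2); accrual 670, randomized 1:1.

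**1. Where 670 comes from**
- 400 / 0.60 = 667, which rounds to 670. As a check, 670 × 0.60 / 2 = 201 per arm.
- The 45% rate plays no part in this figure.

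**2. What 670 yields at T2**
- 670 × 0.45 / 2 = 150.75, which is the plan's 150 per arm.

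**3. Power for T0–T2 knowledge**

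Formula: power ≈ Φ(difference / SE − 2.807), with SE = √((SD₁² + SD₂²)/n). Here SD₁² + SD₂² = 18.49 + 9.30 = 27.79.

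| n per arm | SE | difference / SE | Power, normal | Power, Welch t | Plan |
|---|---|---|---|---|---|
| 150 | 0.430 | 3.39 | 72.1% | 71.2% | 72% |
| 194 | 0.378 | 3.86 | 85.3% | 84.8% | 85% |
| 200 | 0.373 | 3.92 | 86.6% | 86.2% | 86% |

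The plan's figures reproduce. The smallest n for 85% is 193 (normal) or 195 (Welch), against the plan's 194.

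**4. Power for T0–T2 cancer-specific distress at 150 per arm**
- SE = √((2.34 + 8.18)/150) = 0.265, and 1.17 / 0.265 = 4.42.
- Power is 94.6% (normal) or 94.2% (Welch), against the plan's 95%. For this outcome the claim that power is maintained is true.

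**5. What 85% for T0–T2 knowledge would require**
- At 45% completion: 2 × 194 / 0.45 = 862.2, so 863 patients. For the full 200 per arm: 400 / 0.45 = 888.9, so 889 patients.
- At 670 patients: completion of T0 and T2 of 388 / 670 = 58%.

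**6. Sensitivity to the T0–T2 completion rate at 670 patients (Welch)**

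| Completion | n per arm | Power |
|---|---|---|
| 40% | 134 | 64.5% |
| 45% | 150 | 71.2% |
| 50% | 167 | 77.3% |
| 55% | 184 | 82.3% |
| 60% | 201 | 86.4% |

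Of these, only the T0–T1 rate of 60% would make the claim true for knowledge.

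**The case against.** The strongest defence is disclosure. The sentence straight after the claim gives the 45% rate, the 150 per arm and the 72%, and the table repeats it, so anyone who reads the whole paragraph learns the true figure. The 85% was conditional on 200 evaluable pairs per arm, and under that condition it is correct. The 200-per-arm goal is itself qualified as applying at least to T0–T1. The accrual sentence speaks of sufficient power without a number, and its back-reference could be read as identifying which changes are meant, not which power level.

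Most of this stands, and it makes the point minor. It does not remove it. The qualifier attaches to the evaluable goal, whereas the later clause still names T0–T2 knowledge as an analysis whose power is kept. The only power level in the paragraph referred to is at least 85%.

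Stronger readings that a reader might infer are not supported:

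- **That the plan miscalculated or concealed power.** Every figure used here reproduces, and the 72% is printed twice.
- **That the opening of Section 7 makes the same false claim.** It ties 670 to T0–T1 completion and speaks only of sufficient power in general.
- **That just one of the five T0–T2 analyses reaches 85%.** The table's 23% for state anxiety at 150 per arm does not follow from its printed means: −2.43 against 5.00 gives 99.9%, and 23% needs a difference near 2.57. The PROMIS figure of 91% at 0.33 SD and 200 per arm recomputes to about 68% at alpha 0.005. Both are separate problems, so no count is safe until they are reconciled. In any case, Section 7.1.1 does not claim 85% for T0–T2 state anxiety or PROMIS.

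**Conclusion.** The point holds as a minor internal contradiction confined to one clause of Section 7.1.1. For T0–T2 knowledge, 670 patients give about 71–72% power against the 85% referred to, a shortfall of about 13 points. T0–T2 cancer-specific distress, named in the same clause, is unaffected at about 95%.

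This rests on the pilot change scores and SDs as printed, on T0–T2 completion staying near the 45% seen in May 2018, and on reading the back-reference as including the power level. If the back-reference only identifies the outcomes, the clause is loose, not false, and the same rewording still serves. The finding does not show that the trial must enrol more patients; accepting 72% for one of ten primary analyses is open to the sponsor if it says so.

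**What to change.** Reword the accrual paragraph of Section 7.1.1:

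- Remove T0–T2 knowledge from the analyses whose power 670 patients are said to maintain.
- State that 670 is sized on completion of T0 and T1.
- State that, at 45% completion of T0 and T2 (about 150 per arm), T0–T2 cancer-specific distress keeps about 95% power and T0–T2 knowledge is accepted at about 72%.

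Restate T0–T2 power at 150 per arm for PROMIS and state anxiety only after the PROMIS 91% figure and the T0–T2 state anxiety row have been reconciled.

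The cost is wording only. Accrual, analysis and patient procedures do not change. The one consequence is that a power statement becomes less favourable, using a figure the plan already prints.

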While the original education was delivered via a health educator, this approach was chosen to maximize patient feedback regarding key elements and content. We had originally envisioned that it could be adapted for delivery by alternative modalities (e.g. print, web), if acceptable to patients. As an example, in the ongoing RESPECT study (R01-CA190871:[name]), we have adapted provider-mediated tiered-binned pre-disclosure counseling for return of individual research results to an on-line genetic education followed by remote counseling with a genetic counselor at the time of result disclosure to address patient burdens associated with in-person visits. The ongoing multi-site RESPECT study will evaluate the outcomes of receipt of individual germline research results with this alternative delivery model.

To date, 25 breast cancer patients have enrolled in the COMET pilot study. 20 have completed genetic education and post-education

surveys. 14 have received results and have completed post-disclosure surveys.

Key preliminary findings relevant to this proposal include:

1. Many patients reported a limited understanding of the difference between germline and somatic genetics and the limitations of tumor profiling (e.g. the potential for no druggable targets).
2. Participants reported greater interest in web-based administration as an alternative to provider-mediated counseling than print materials. Patients reported advantages to web-based education included convenience, the ability to revisit information, faster access and the individual ability to select information to view. Many reported no disadvantages to a web-based alternative, while some identified losing the personal interaction, getting confused or not knowing what to view on a website.
3. Preliminary data suggests pre-disclosure genetic education may be associated with increases in knowledge and decreases in depression and general and state anxiety from baseline to post-disclosure.

In this pilot, there was no comparison arm, so changes in these outcomes need to be evaluated in a randomized study.

1.5.2 Secondary Genetic Counseling Substudy - Genetic Counseling for Incidental Germline Findings (Step 2):

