IES-Total	T0 to T1	46	85%	0.29	-1.78	1.70	3.19
Knowledge	T0 to T1	100	97%	1.70	-1.50	6.11	3.02
Knowledge	T0 to T1	150	100%	1.70	-1.50	6.11	3.02
Knowledge	T0 to T1	200	100%	1.70	-1.50	6.11	3.02
Knowledge	T0 to T1	300	100%	1.70	-1.50	6.11	3.02
Knowledge	T0 to T1	400	100%	1.70	-1.50	6.11	3.02
Knowledge	T0 to T1	68	85%	1.70	-1.50	6.11	3.02
State Anxiety	T0 to T2	100	13%	-2.43	5.00	4.04	14.58
State Anxiety	T0 to T2	150	23%	-2.43	5.00	4.04	14.58
State Anxiety	T0 to T2	200	34%	-2.43	5.00	4.04	14.58
State Anxiety	T0 to T2	300	55%	-2.43	5.00	4.04	14.58
State Anxiety	T0 to T2	400	72%	-2.43	5.00	4.04	14.58
State Anxiety	T0 to T2	512	85%	-2.43	5.00	4.04	14.58
IES-Total	T0 to T2	100	79%	-1.00	-2.17	1.53	2.86
IES-Total	T0 to T2	150	95%	-1.00	-2.17	1.53	2.86
IES-Total	T0 to T2	200	99%	-1.00	-2.17	1.53	2.86
IES-Total	T0 to T2	300	100%	-1.00	-2.17	1.53	2.86
IES-Total	T0 to T2	400	100%	-1.00	-2.17	1.53	2.86
IES-Total	T0 to T2	114	85%	-1.00	-2.17	1.53	2.86
Knowledge	T0 to T2	100	48%	5.86	4.40	4.30	3.05
Knowledge	T0 to T2	150	72%	5.86	4.40	4.30	3.05
Knowledge	T0 to T2	200	86%	5.86	4.40	4.30	3.05
Knowledge	T0 to T2	300	98%	5.86	4.40	4.30	3.05
Knowledge	T0 to T2	400	100%	5.86	4.40	4.30	3.05
Knowledge	T0 to T2	194	85%	5.86	4.40	4.30	3.05

Power for Promis Depression and Promis Anxiety

With 200 evaluable patients per arm, there is 91% power to detect an effect size of 0.33 (as fraction of standard deviation), using t-test at two-sided significance level 0.005. Based on data from 92 children/adolescents, Hinds et al. (2012) reported standard deviation of 10.74 for Promis Depression and 12.5 for Promis Anxiety, respectively. Assuming the standard deviations for these two measurements in our proposed study are similar, the following table gives the absolute difference that can be detected with 91% power, under different assumptions for the correlation between the measurements across two timepoints, at two-sided significance level 0.005.

Variable	Correlation	Standard deviation of change	Effect size (as fraction of standard deviation)	Absolute difference	Power
Promis Depression	0.4	11.8	0.33	3.89	91%
Promis Depression	0.6	9.6	0.33	3.17	91%
Promis Depression	0.8	6.8	0.33	2.24	91%
Promis Anxiety	0.4	13.7	0.33	4.5	91%
Promis Anxiety	0.6	11.2	0.33	3.7	91%
Promis Anxiety	0.8	7.9	0.33	2.6	91%

Rev. 7/17

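### The six power rows for state anxiety from T0 to T2 contradict their own inputs: the printed means differ by 7.43, but the printed powers fit a difference of 2.57

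*Combined protocol and SAP*

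**What the plan says.** Section 7.1.1 names ten primary analyses: five outcomes, each as change from T0 to T1 and from T0 to T2. State anxiety from T0 to T2 is one of them. The significance level is Bonferroni-adjusted ("5% Typical Type I error rate / 10 comparisons = 0.5% nominal p-value for declaring statistical significance"), and power is calculated "using t test at two-sided 0.005 significance level".

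The table of power by sample size gives this analysis six rows. All six print mean changes of -2.43 and 5.00 and SDs of 4.04 and 14.58. At 200 per arm the row is "State Anxiety T0 to T2 200 34% -2.43 5.00 4.04 14.58". The last row gives the sample size for 85% power: "State Anxiety T0 to T2 512 85% -2.43 5.00 4.04 14.58". The other rows print 13% at 100 per arm, 23% at 150, 55% at 300 and 72% at 400.

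The text of Section 7.1.1 says of 200 evaluable patients per arm: "which provides at least 85% power for all short-term outcomes (e.g. T0-T1) and changes in knowledge and cancer specific distress" after tumor profiling results. State anxiety from T0 to T2 is not on that list. For the lower T0 to T2 completion rate, the text says "the projected evaluable sample size of 150 patients/arm can give the power of 72% for changes in knowledge and 95"% for cancer specific distress. It gives no figure for state anxiety.

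The state anxiety, IES-Total and knowledge inputs are attributed to the COMET pilot. Section 1.5.1 says of that pilot: "In this pilot, there was no comparison arm, so changes in these outcomes need to be evaluated in a randomized study". It also reports that "14 have received results and have completed post-disclosure surveys".

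**The concern.** A mean difference of 7.43 with these SDs is about 0.7 of the root-mean-square SD of 10.7. An effect of that size does not need 512 patients per arm for 85% power, even at the 0.005 level. Either the printed means or the printed powers are wrong.

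The two readings lead to different conclusions from the trial. If power is about 23%, a non-significant result for this primary comparison says very little. If power is about 99.9%, the same result is strong evidence against the planned effect. No other part of the plan states the power for this analysis, so a reader cannot tell which holds. The assumed direction is also unsettled: 2.43 against 5.00 puts Group 2 higher, whereas -2.43 against -5.00 puts Group 1 higher.

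**Working it through.** **Inputs** (all from Section 7.1.1): two-sided alpha 0.005, so z(0.9975) = 2.807; 1:1 allocation; printed means and SDs. For 85% power, z(0.85) = 1.036.

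**Formulas** (normal approximation, n per arm):

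- SE = sqrt((SD1² + SD2²) / n)
- Power = Phi(|difference| / SE - 2.807)
- n for 85% = (2.807 + 1.036)² × (SD1² + SD2²) / difference²

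**Step 1. Does this method reproduce the rest of the table?** Yes.

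- Knowledge, T0 to T2, 150 per arm: difference 5.86 - 4.40 = 1.46; SE = sqrt((4.30² + 3.05²)/150) = 0.430; power = Phi(3.392 - 2.807) = 72.1%. Printed: 72%.
- IES-Total, T0 to T2, 150 per arm: difference 1.17; SE = sqrt((1.53² + 2.86²)/150) = 0.265; power = Phi(4.418 - 2.807) = 94.6%. Printed: 95%.
- All 30 rows of the other five blocks agree within 1 percentage point. The sample sizes for 85% come out at 61, 46, 68, 114 and 193, against 61, 46, 68, 114 and 194 printed.

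**Step 2. State anxiety, T0 to T2, from its printed inputs.**

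- Difference = 5.00 - (-2.43) = 7.43.
- SD1² + SD2² = 4.04² + 14.58² = 228.90.
- n = 100: SE = 1.513; power = Phi(4.911 - 2.807) = 98.2%.
- n = 150: SE = 1.235; power = Phi(6.015 - 2.807) = 99.9%.
- n for 85% = 3.843² × 228.90 / 7.43², which rounds up to 62 per arm.

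**Step 3. Which difference do the printed powers imply?** Solving (z(power) + 2.807) × SE for each row gives 2.543, 2.555, 2.562, 2.562, 2.564 and 2.570. Allowing for rounding of the printed percentages, the range that fits all six rows is 2.556 to 2.573. It contains 5.00 - 2.43 = 2.57.

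| n per arm | Printed power | Difference 7.43 | Difference 2.57 |
|---|---|---|---|
| 100 | 13% | 98.2% | 13.4% |
| 150 | 23% | 99.9% | 23.4% |
| 200 | 34% | >99.9% | 34.3% |
| 300 | 55% | >99.9% | 55.4% |
| 400 | 72% | >99.9% | 72.3% |
| 512 | 85% | >99.9% | 85.0% |
| n for 85% | 512 | 62 | 512 |

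**Step 4. Could something else explain it?**

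- *Exact test.* The Welch noncentral t calculation gives 97.8% at 100 per arm and n = 65 for a difference of 7.43. For 2.57 it gives 12.8, 22.7, 33.5, 54.7, 71.8 and 84.7% down the rows, and n = 516. The conclusion is the same.
- *Other settings with 7.43, at 100 per arm.* One-sided alpha gives 99.0%, alpha 0.0005 gives 92.4%, SD 14.58 in both groups gives 78.7%, and reading n as the total gives 74.7%. None is near 13%.
- *A wrong SD.* Keeping 7.43 would need a root-mean-square SD of 30.9 to 31.3. The printed SDs give sqrt(228.90/2) = 10.7.

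**The case against.** The arithmetic is hard to dispute. The case on the other side concerns diagnosis and weight.

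- *The sign error is inferred.* The powers fix only the absolute difference. A wrong value for either mean that happened to give about 2.57 would fit equally well. This stands: a sign error is the most likely cause because 5.00 - 2.43 falls inside a narrow range, but it is not proved. The fix must allow for other values.
- *The text sides with the powers.* Section 7.1.1 claims at least 85% power from T0 to T2 only for knowledge and cancer specific distress, which agrees with 34% at 200 per arm. This makes the means the more likely culprit. It does not settle the matter, because the text may simply have been written from a wrong power column.
- *Nothing in the design depends on these rows.* This is correct. The accrual goal comes from 200 per arm and 60% completion of T0 and T1 (400 / 0.60 = 667, set at 670). If 7.43 is right, the printed powers err on the cautious side. This limits the weight of the point but does not remove the contradiction.
- *The undefined groups and the small pilot are separate matters.* This is largely fair. Both affect every pilot-based row, and the count of 14 is an interim one that the plan does not tie to this table. They add uncertainty about the inputs and are not part of the arithmetic error.

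**Conclusion.** The six rows are wrong as printed. With the stated means, SDs and alpha, power is about 98% at 100 per arm and at least 99.9% from 150 upwards. The required sample size for 85% power is overstated about eightfold (512 against 62, or 65 by Welch). With an absolute difference of 2.57, all six rows are right and at least one printed mean is wrong.

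At the projected 150 evaluable patients per arm, the planned power of this primary analysis is therefore about 23% or about 99.9% under the two readings that the table supports. The documents do not show which applies. The contradiction itself needs no outside assumption; only its attribution to a sign error is inferred. The effect is local to this block and to the sentence listing the adequately powered outcomes. It should be corrected, but it does not touch the sample size, the alpha or the test.

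**What to change.** Check both means, -2.43 and 5.00, against the pilot data. Then:

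- If the absolute difference is 2.57, correct the wrong mean in all six rows, and state in Section 7.1.1 that state anxiety from T0 to T2 has about 23% power at the projected 150 per arm.
- If it is 7.43, replace the powers at 100, 150, 200, 300 and 400 per arm, change the sample size for 85% from 512 to about 62 (65 by Welch), and add this analysis to the outcomes listed with at least 85% power.
- If the pilot gives other values, recompute the six rows from them and adjust the text to match.

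In the same edit, say what Group 1 and Group 2 stand for, since the pilot had no comparison arm.

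The cost is a check of two values (assuming the pilot data are on file), one corrected table block, a short definition of the groups and one added phrase in Section 7.1.1. The 200 per arm and 670 targets, the alpha and the test stay as they are.

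### PROMIS anxiety and depression have about 68% power at two-sided 0.005 (200 per arm, 0.33 SD), not the stated 91%, so the 85% claim for T0–T1 outcomes fails for both

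*Combined protocol and SAP*

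**What the plan says.** Section 7.1.1 names ten primary analyses: five outcomes, each as change from T0 to T1 and from T0 to T2. PROMIS anxiety and PROMIS depression are two of the five. The significance level is Bonferroni-adjusted: "5% Typical Type I error rate / 10 comparisons = 0.5% nominal p-value for declaring statistical significance".

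The section justifies 200 evaluable patients per arm as a number "which provides at least 85% power for all short-term outcomes (e.g. T0-T1"), and adds knowledge and cancer specific distress from T0 to T2, all "using t test at two-sided 0.005 significance level".

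The PROMIS outcomes get their own calculation, for this reason: "As there was no preliminary data for Promis Depression/Anxiety in a similar setting". Standard deviations of 10.74 (depression) and 12.5 (anxiety) are taken from a cited study of 92 children and adolescents. The paragraph opens "With 200 evaluable patients per arm" and continues "there is 91% power to detect an effect size of 0.33 (as fraction of standard deviation), using t-test at two-sided significance level 0.005". It then says that "the following table gives the absolute difference that can be detected with 91% power", for correlations of 0.4, 0.6 and 0.8, again at two-sided 0.005. All six rows show an effect size of 0.33 and power of 91%.

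**The concern.** With 200 per arm and 0.33 SD, 91% is the familiar answer for a conventional two-sided 5% test. A level ten times stricter must cost a good deal of power, so 91% cannot also be right at 0.005.

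The figure is relied on. It is the only support for including PROMIS in the 85% claim, and that claim is the stated reason for 200 evaluable per arm. The accrual increase to 670 was in turn set to keep that number. Lower distress is a primary objective (Section 2.1.1), and PROMIS supplies two of its four measures. Someone weighing a non-significant PROMIS result against a planned 91% would credit the trial with more sensitivity than it has.

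**Working it through.** **Inputs (all from Section 7.1.1):** 200 evaluable per arm, 1:1 allocation, standardised difference d = 0.33 in change scores, t-test, two-sided level 0.005.

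**1. Where 91% comes from.** The noncentrality is d × √(n/2) = 0.33 × √100 = 3.30, with 398 degrees of freedom. At two-sided 0.05 the normal approximation gives Φ(3.30 − 1.960) = Φ(1.340) = 91.0%; the noncentral t gives 90.9%. This is the printed figure.

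**2. Power at the stated level.** At two-sided 0.005 the normal approximation gives Φ(3.30 − 2.807) = Φ(0.493) = 68.9%. The noncentral t gives 68.3%, and a 40,000-replicate simulation of the planned unequal-variance test gives 68.5%. One-sided 0.005 gives only 76–77%, and a one-sample or paired test with n = 200 gives 96.5%, so neither explains the figure.

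**3. Is 0.33 a misprint?** The SD of change is SD × √(2(1 − r)).

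| Outcome | r | SD of change | 0.33 × SD | Printed difference |
|---|---|---|---|---|
| Depression | 0.4 | 11.77 | 3.88 | 3.89 |
| Depression | 0.6 | 9.61 | 3.17 | 3.17 |
| Depression | 0.8 | 6.79 | 2.24 | 2.24 |
| Anxiety | 0.4 | 13.69 | 4.52 | 4.5 |
| Anxiety | 0.6 | 11.18 | 3.69 | 3.7 |
| Anxiety | 0.8 | 7.91 | 2.61 | 2.6 |

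The rows agree to rounding, so 0.33 really was used. Only the pairing of power with level is wrong.

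**4. Was 0.005 used elsewhere in the section?** For knowledge, T0–T2, 200 per arm: SE = √((4.30² + 3.05²)/200) = 0.373; 1.46/0.373 = 3.92; Φ(3.92 − 2.807) = 87%. The noncentral t gives 86.2%. The plan prints 86%; at 0.05 it would be 97.4%. For knowledge, T0–T1, 100 per arm, the recomputed value is 96.6% (printed 97%; 99.7% at 0.05). For state anxiety, T0–T1, 100 per arm, it is 98.2% (printed 98%; 99.9% at 0.05). These rows use 0.005.

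**5. Does the higher accrual close the gap?** 670 × 0.60 / 2 = 201 evaluable per arm, which gives 68.6%.

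**6. What 200 per arm can detect at two-sided 0.005 (noncentral t).** The effect is 0.386 SD for 85% power and 0.417 SD for 91%. Multiplying 0.417 (0.4168 unrounded) by the SDs of change gives, for r = 0.4/0.6/0.8, 4.90/4.00/2.83 points for depression and 5.71/4.66/3.30 for anxiety. For scale, holding 0.33 SD would take 274 per arm for 85% power and 318 for 91%.

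**The case against.** The arithmetic is not in dispute. The case on the other side concerns how much it matters.

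- **0.33 SD is not a justified target.** The plan gives no expected PROMIS effect and no minimally important difference; the table is a statement of what can be detected. The error can therefore be described as understating the detectable effect (0.33 instead of 0.417 SD), not as a failure to power for a predicted one. That is fair, and the 32% miss rate holds only if the true difference is 0.33 SD. But the plan still claims at least 85% power for these outcomes, and it offers no other effect size to support that.
- **Conduct is unaffected, and low power is accepted elsewhere.** The plan openly reports 72% for knowledge T0–T2 at 150 per arm, and prints 34% for state anxiety T0–T2 at 200 per arm. That limits the harm. The difference is that those shortfalls are disclosed and this one is not. Nor does the plan say how a non-significant PROMIS result would be read, so over-reading is a risk, not a stated intention.
- **Not every pilot row reproduces.** The state anxiety T0–T2 rows print changes of −2.43 and 5.00, which give 97.8% at 100 per arm against a printed 13%. The printed power fits a difference of 5.00 − 2.43 = 2.57. This is a separate problem with those rows. Their powers still correspond to 0.005, so the comparison in step 4 stands for the rows named there.

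**Conclusion.** The stated PROMIS power is wrong. With 200 per arm, 0.33 SD and two-sided 0.005 it is 68%, about 23 percentage points below the printed 91%. The most likely cause is use of the unadjusted 0.05 level; the documents do not show this directly, but the match is close (90.9%).

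At 0.33 SD the claim of at least 85% power for all T0–T1 outcomes falls short by about 17 points for PROMIS anxiety and PROMIS depression. It would hold only for true effects of about 0.386 SD or more. At 91% power the detectable differences are understated by about a fifth (0.33/0.417 = 0.79).

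The result assumes normally distributed change scores, equal variances and equal arms. It does not depend on the borrowed SDs, since power is set by the standardised effect; those SDs affect only the differences in points. The statements on knowledge and cancer specific distress from T0 to T2 at 200 per arm are correct.

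**What to change.** Correct the PROMIS paragraph and table in Section 7.1.1 in one of two ways:

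- **(a) Keep 0.33 SD.** Replace 91% with 68% in the text and in all six rows. In the sample-size sentence, limit the T0–T1 part of the 85% claim to state anxiety, cancer specific distress (IES) and knowledge.
- **(b) Keep 91%.** Replace 0.33 with 0.417 SD, and the absolute differences with 4.90/4.00/2.83 (depression) and 5.71/4.66/3.30 (anxiety) for r = 0.4/0.6/0.8. The 85% sentence can then stay, provided it is read against the restated PROMIS effect.

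Under either option, leave the T0–T2 part of that sentence as it is.

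The cost is one table and one or two sentences. The test, the 0.005 threshold and the accrual goal of 670 stay the same, and no extra patients are needed. The price is a less favourable PROMIS statement: lower power, or a larger detectable difference.
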